All medications, including over-the-counter treatments and preventative vaccines taken by the patient during the study, including those treatments initiated prior to the start of the study, must be recorded in the CRF. The entry must include the dose, regimen, route, indication, and dates of use.

Study Procedures

Table 2 outlines the timing of procedures, and assessments to be performed throughout the study.

Table 2. Schedule of Assessments

Visit Number	1	2	3	4	5	6
Days	N/A	Day 0	Day 3	Day 7	Day 10	Day 28
Visit Name	Screening	Baseline/ Infusion 1	Infusion 2	Infusion 3	Infusion 4	End of Study / Telephone Encounter**
Window Period	Up to 7 days	±3 days	±3 days	±3 days	±3 days	±3 days
STUDY PROCEDURES						
Informed Consent	X					
Demographics	X					
Inclusion and Exclusion Criteria	X					
Medical History Review	X	X	X	X	X	X
Concomitant Medication Review	X	X	X	X	X	X
Eligibility	X					
Randomization	X					
Adverse Event Monitoring		X	X	X	X	X
ASSESSMENTS						
Vital Signs	X	X	X	X	X	
Weight and Height ¹	X	X	X	X	X	
Physical Examination	X	X	X	X	X	
Ordinal Scale		X	X	X	X	X
CBC with differential	X	X	X	X	X	
Comprehensive Metabolic Panel	X	X	X	X	X	
Coagulation Panel	X	X	X	X	X	
Urinalysis with pregnancy test (childbearing age women only)	X					
PCR test for SARS-CoV-2		X	X	X	X	
Exploratory Laboratory Assessments ²		X	X	X	X	
Inflammatory Marker Laboratory Assessments ³		X	X	X	X	
EKG		X*	X*	X*	X*	
CT Scan		X				X
Chest X Ray (PA, Single View) ⁴		X				X
ADMINISTRATION						
Allogeneic HB-adMSCs Administration		X	X	X	X	

1. Height will only be measured at screening

2. Exploratory laboratory Assessments: Natural Killer Cell Surface Antigen (CD3-CD56+ Marker Analysis), Troponin, Myoglobin, Creatine Kinase (CK) MB, Serum ferritin, CD4+/CD8+ ratio, D-dimer

3. Inflammatory Marker Laboratory assessments: CRP, IL-6, IL-10, TNFa

4. Chest Xray and CT scan will be performed as scheduled, however, if the patient is discharged prior to the scheduled tests at 28 days, any imaging (CT/Xray) done at discharge

* Subsequent EKG will be performed if necessary, such as abnormal result at baseline

** Telephone encounter is conducted if subject has been discharged

Informed Consent (ICF)

Prior to commencement of any trial related activity, the investigator or designated staff will obtain written informed consent from the patient or their Legally Authorized Representative (LAR).

Patient Re-Screening

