9.3.5 Unscheduled Visits

The Investigator may at his/her discretion arrange for a patient to have an unscheduled assessment, especially in the case of adverse events (AEs) that require follow-up, or an AE considered by the Investigator to be possibly related to the use of the investigational product. The unscheduled visit page in the CRF must be completed.

10. Efficacy Assessments

7-Point Ordinal Scale

The ordinal scale is an assessment of the clinical status at the first assessment of a given study day. The scale is as follows:

- 1) Death
- 2) Hospitalized, on invasive mechanical ventilation or extracorporeal membrane oxygenation (ECMO)
- 3) Hospitalized, on non-invasive ventilation or high flow oxygen devices
- 4) Hospitalized, requiring supplemental oxygen
- 5) Hospitalized, not requiring supplemental oxygen
- 6) Not hospitalized, limitation on activities
- 7) Not hospitalized, no limitations on activities.

Complete Blood Count with Differential

The evaluation of the Complete Blood count with differential will help suspect the presence of a bacterial or viral infection with the predominance of either the neutrophils or lymphocytes. Generally, a healthy person’s blood count would not show out of range values in the differential in the absence of a pathological condition.

Comprehensive Metabolic Panel

The evaluation of glucose, calcium, proteins, electrolytes, liver enzymes and kidney function to determine status of metabolism. This panel is used to determine if treatments are having an effect on metabolic function.

CRP

C-reactive protein is considered to be an "acute phase protein," an early indicator of infectious or inflammatory conditions. CRP must be interpreted in the clinical context; no single value will be used to rule in or rule out a specific diagnosis.

CD4+/CD8+ ratio

The CD4+/CD8+ ratio is the ratio of T helper cells (with surface marker CD4) to cytotoxic T cells (with surface marker CD8). The CD4+/CD8+ ratio in the peripheral blood of healthy adults and mice is about 2:1, an inverted CD4+/CD8+ ratio (namely, less than 1/1) indicates an impaired immune system. A reduced CD4+/CD8+ ratio is associated with reduced resistance to infection, with ageing, and is an indicator of immunosenescence.

Natural Killer Cell Surface Antigen (CD3-CD56+ Marker Analysis)

Percentage CD3-CD56+ natural killers (NK⁺); absolute CD3-CD56+ natural killers (NK⁺); absolute lymphocyte count.

TNF-a

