The primary role of TNF is in the regulation of immune cells. TNF, being an endogenous pyrogen, is able to induce fever, apoptotic cell death, cachexia, inflammation and to inhibit tumorigenesis and viral replication and respond to sepsis via IL1- & IL6-producing cells.

IL-6

Interleukin 6 (IL-6) is an interleukin that acts as both a pro-inflammatory cytokine and an anti-inflammatory cytokine. In humans, it is encoded by the *IL6* gene.

IL-10

IL-10 is a cytokine with multiple effects in immunoregulation and inflammation. It downregulates the expression of Th1 cytokines, MHC class II antigens, and co-stimulatory molecules on macrophages. It also enhances B cell survival, proliferation, and antibody production.

VEGF

VEGF is vascular endothelial growth factor. It is a signal protein produced by cells to stimulate angiogenesis. Increased levels of VEGF in the blood can indicate increased inflammation.

D-dimer

D-dimer is a protein fragment produced by dissolution of blood clots. Levels detectable in blood indicate clot formation and degradation within the system.

Myoglobin

A cytoplasmic protein that binds oxygen on a heme group. Functions to store oxygen. Increased myoglobin occurs when muscle tissue is damaged.

Troponin

A regulatory protein involved in muscle contraction. Can be used to indicate damage to myocardium. Increased troponin indicates recent cardiac muscle damage.

Creatinine Kinase

An enzyme involved in conversion of creatine in tissues that rapidly consume ATP, such as muscle. Higher levels of creatinine kinase are measured in the blood to identify damage to these tissues, such as myocardial infarction.

Serum Ferritin

An intracellular protein involved in iron storage. This test is generally used as a diagnostic for iron-deficiency anemia. High levels of serum ferritin may also indicate an acute inflammatory reaction, such as infection.

PCR nasopharyngeal swab

To detect viral target for Human Coronavirus (SARS-CoV-2), which would indicate active infection. If a subject with a previous positive PCR result obtains two negative PCR results consecutively, they are considered clear of active infection.

Safety Assessments

Safety assessments (vital signs, weight, physical examinations, EKG recordings, AEs, routine clinical laboratory tests (CBC, CMP, PT, PTT/INR and urinalysis) and chest x-rays will be performed at the visits specified in the schedule of assessments in Table 2.

Vital Signs, Height, and Weight

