The Investigator must review all laboratory reports and document the review. Any laboratory test result or change considered by the Investigator to be clinically significant should be considered an AE and recorded in the AE CRF. Clinically significant abnormal values occurring during the study will be followed until repeat test results return to normal, stabilize, or are no longer clinically significant.

Laboratory tests to be performed during the study:

Complete Blood Count with Differential	Natural Killer Cell Surface Antigen (CD3 ⁻ CD56 ⁺ Marker Analysis)
Complete Metabolic Profile	Il-10
Coagulation study (PTT/PT/INR)	CD4+ / CD8+ ratio
Urinalysis with pregnancy test	Creatine Kinase (CK)
C Reactive Protein	Troponin
Tumor Necrosis Factor alpha	Myoglobin (MB)
D-Dimer	VEGF
	Serum Ferritin

Adverse Events

An AE is any symptom, physical sign or disease that either emerges during the study or, if present at screening, worsens during the study, regardless of the suspected cause of the event. All medical and psychiatric conditions (except those related to the indication under study) present at screening will be documented in the medical history CRF. Changes in these conditions and new symptoms, physical signs, or diseases should be noted on the AE CRF during the rest of the study.

Clinically significant laboratory abnormalities should also be recorded as AEs. Surgical procedures that were planned before the patient enrolled in the study are not considered AEs if the conditions were known before study inclusion; the medical condition should be reported in the patient's medical history. Changes from baseline respiratory rate for non-ventilated subjects should also be considered as AE.

Serious Adverse Events (SAE)

A serious adverse event (SAE) is any AE that is:

- fatal
- life-threatening
- requires or prolongs hospital stay
- results in persistent or significant disability or incapacity
- Important Medical Events (IME): those events that may not result in death, be immediately life threatening, or require hospitalization. They may be considered a SAE when, based upon medical judgement, they may jeopardize the subject and may require intervention to prevent one of the other serious outcomes noted above. For example, drug overdose or abuse, a seizure that did not result in in-patient hospitalization, or intensive treatment of bronchospasm in an emergency department would typically be considered serious. (FDA, 21CFR312.32; ICH E2A and ICH E6)

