Safety is assessed by primary and secondary endpoints. Primary safety endpoints include incidence of adverse and serious adverse events. Secondary safety endpoints include incidence of specific adverse events including serious infections, infusion-related reactions, hepatotoxicity, heart failure, and cytopenias. Clinically significant changes in laboratory values, vital signs, weight, and physical examination results will also be measured.

Clinical efficacy is assessed by primary and secondary endpoints. Primary endpoints include the change from baseline in inflammatory markers (IL-6, D-dimer, C Reactive protein), time to clearing PCR test, change from baseline oxygenation, and time to return to room air (RTRA). Secondary endpoints include change from baseline of chest x-ray, change from baseline of CT scan, change from baseline of clinical laboratory values, adverse and serious adverse events, change in exploratory markers, and change in ordinal scale.

Analysis Population

Safety: All subjects receiving at least one infusion will be included for safety analysis.

Efficacy: All subjects receiving all four infusions will be included for efficacy analysis.

Additional sub-analysis will be performed comparing subjects receiving any other experimental treatment for COVID-19, to those who are not, in the following items:

- Change from baseline oxygenation
- Change from baseline chest x-ray
- Change from baseline CT scan
- Time to clearing PCR test
- Change from baseline inflammatory markers (IL-6, D-dimer, C Reactive protein)
- Change from baseline in IL-10
- Change from baseline in CD4:CD8 ratio
- Change from baseline in CD3⁺CD56⁺
- Change from baseline in VEGF
- Change from baseline in the 7-point ordinal scale

Demographic and Baseline Characteristics

Information describing subjects' gender, race/ethnicity, and age will be displayed in tables similar to the ones included below. The number and percent of the total sample population will be calculated for each demographic category.

Demographics	Female		Male		Both Genders	
Race/Ethnicity	N	%	N	%	Total	%
White						
Black or African American						
Hispanic or Latino						
Other (Specify)						
Total						

The mean, minimum, and maximum age at enrollment will be determined using standard calculations. The number and percent of total subjects in each age group will be calculated and reported.

Age at Enrollment	N	%
Mean		
Minimum		
Maximum		
	N	%
≥ 18 years		
18-21 years		
22-29 years		
30-39 years		

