## 7.2. Secondary Efficacy Analyses

### 7.2.1. Endpoints / Variables

Change from baseline through Visit 5 (Day 10):

- Change in clinical laboratories
- Change from baseline in exploratory markers (D-dimer, myoglobin, troponin, creatinine kinase, serum ferritin, CD3CD56, CD4/CD8, VEGF)

Change from baseline through Visit 6 (Day 28):

- Change from baseline Chest X-ray (available at Visit 6 only)
- Change from baseline CT scan (available at Visit 6 only)
- Time to negative PCR test results
- Change from baseline in the 7-point ordinal scale

Cumulative:

- Cumulative incidence of serious adverse events (SAEs) or adverse events (AEs)

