#### **7.2.4.2. Data Analytic Models**

All secondary endpoint efficacy measurements available at post-baseline at scheduled measurements (Visits 2 through 5 [infusions 1 through 4] for exploratory markers and clinical labs; Visits 2 through 6 [infusion 1 through end of treatment] for chest X ray, CT scan, and ordinal scale score) will be analysed in a generalized linear mixed model. The model will predict each outcome as a function of the interaction between the fixed factors treatment group and time, controlling for lower order effects of time and treatment group. Models will control for stratification variables (see [Covariates and Other Strata](#)), and subject will be included as random effects. AEs/SAEs and AE severity will be analyzed as dichotomous outcomes (whether patient exhibited AE/SAE at any time during the study). AE/SAE attribution to study drug will be analyzed as count outcomes. All models will control for stratification variables.

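### VEGF is a secondary endpoint with no collection visit in the protocol's schedule, and the creatine kinase analyte is named inconsistently

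*Protocol*

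**What the plan says.** SAP 7.2.1 lists as a secondary endpoint, through Day 10, "Change from baseline in exploratory markers (D-dimer, myoglobin, troponin, creatinine kinase, serum ferritin, CD3CD56, CD4/CD8, VEGF". The same eight markers appear in SAP 2.1 and in the protocol's Synopsis and Study Endpoints. SAP 7.2.4.2 takes "Visits 2 through 5 [infusions 1 through 4] for exploratory markers and clinical labs" into the longitudinal model.

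The protocol ticks two marker panels at Days 0, 3, 7 and 10 in Table 2 and defines them in footnotes. Footnote 2 reads "Exploratory laboratory Assessments: Natural Killer Cell Surface Antigen (CD3-CD56+ Marker Analysis), Troponin, Myoglobin, Creatine Kinase (CK) MB, Serum ferritin, CD4+/CD8+ ratio, D-dimer". Footnote 3 reads "Inflammatory Marker Laboratory assessments: CRP, IL-6, IL-10, TNFa". Neither contains VEGF.

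A second list, under Clinical Laboratory Parameters, is headed "Laboratory tests to be performed during the study". It includes VEGF and gives creatine kinase as CK, with the letters MB placed after myoglobin instead. It has no visit columns. The Efficacy Assessments section describes VEGF, also without a visit, and describes creatine kinase in general terms: "An enzyme involved in conversion of creatine in tissues that rapidly consume ATP, such as muscle".

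SAP 5.3 takes the last non-missing pre-treatment value as baseline, allows a screening value if Day 0 is missing, and otherwise leaves baseline missing with nothing derived.

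**The concern.** An endpoint defined as a change from baseline needs a sample before the first infusion. Site staff order blood tests from the schedule of assessments, and that schedule does not ask for VEGF at any visit. A pre-treatment sample that was not taken cannot be obtained later, so an omission in one footnote can remove the endpoint.

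The creatine kinase problem is different in kind. Something will be measured, but the documents do not fix what. CK-MB is one isoenzyme of creatine kinase, so a change in CK-MB and a change in total CK are different quantities. If the SAP does not say which one it analyses, the choice is left until results are in hand.

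**Working it through.** No figure in the plan has to be reproduced. The check sets the eight endpoint markers against the two places in the protocol that say what is tested.

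| Endpoint marker | Table 2 (Days 0, 3, 7, 10) | Laboratory list (no visits) |
|---|---|---|
| D-dimer | yes | yes |
| Myoglobin | yes | yes, with MB after it |
| Troponin | yes | yes |
| Serum ferritin | yes | yes |
| CD4/CD8 | yes | yes |
| Creatine kinase | as CK-MB | as CK |
| CD3/CD56, no sign given | as CD3-negative, CD56-positive | as CD3-negative, CD56-positive |
| VEGF | absent | yes |

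Count against Table 2: 5 plain matches + 2 matches with a naming question + 1 absent = 8. Against the laboratory list, all 8 have an entry.

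**VEGF, step by step.**

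1. SAP 7.2.4.2 expects exploratory markers at Visits 2 to 5, which is 4 visits. Table 2 names VEGF at 0 of those 4.
2. The infusion-visit procedures call for blood to be drawn for laboratory tests but name no assay, so they do not fill the gap.
3. The SAP 5.3 fallback does not help. The protocol's Screening section limits blood and urine tests to blood count, chemistry, coagulation and, where relevant, pregnancy. Table 2 schedules no exploratory panel at screening.
4. A patient at a site that follows Table 2 alone therefore has no VEGF baseline. Under SAP 5.3 the baseline is missing and no change is derived.
5. The missing-data modelling in SAP 7.1.4.1 works from observed outcomes. If VEGF was never assayed, there are none to work from.

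**Creatine kinase.** Table 2 says CK-MB. The laboratory list says CK. The endpoint lists in both documents name no isoenzyme. The Efficacy Assessments text does not settle it: it refers to muscle in general and then gives a heart attack as its example. The MB beside myoglobin in the laboratory list may have been moved from the CK entry, but the documents do not show which placement is the mistake.

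**CD3/CD56.** The assay output is "Percentage CD3-CD56+ natural killers (NK⁺); absolute CD3-CD56+ natural killers (NK⁺); absolute lymphocyte count". Table 2 and the laboratory list agree with it. One bullet in the Analysis Population sub-analysis list differs in the sign on CD3: "Change from baseline in CD3⁺CD56". No listed test reports a CD3-positive, CD56-positive population.

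**The case against.** The best answer is that VEGF is a planned test. It is in the laboratory list, it has its own paragraph under Efficacy Assessments, blood is drawn at every infusion visit, and SAP 7.2.4.2 shows that values at Visits 2 to 5 were intended. On that view the footnote is a drafting slip and the samples may well exist. This stands as far as it goes. It rules out saying that the trial never collects VEGF or that the change cannot be derived. It does not supply a visit: the laboratory list has none, and the SAP does not instruct sites.

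A reader might infer that one site would report total CK and the other CK-MB, making the data impossible to pool. The documents do not support that. Both sites work under one protocol, and the section on case report forms refers to a central laboratory. The supportable point is only that the analyte is not fixed.

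A reader might also infer that the CD3/CD56 endpoint has no assay. It does: the endpoint lists give no sign and can be met by the stated assay. The conflict is one superscript, possibly a typing or text-extraction error, in a sub-analysis by other experimental treatment that the SAP's Examination of subgroups does not carry forward.

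Finally, the laboratory list omits IL-6, which might suggest that a primary marker is uncollected. Table 2 footnote 3 schedules it at all four infusion visits, so nothing follows from the omission.

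**Conclusion.** The point holds in a limited form. VEGF is an endpoint and a listed test with no scheduled visit. If Table 2 alone was followed, its change from baseline is lost. Whether that happened cannot be known from the documents. The creatine kinase analyte is undefined across Table 2, the laboratory list, the endpoint lists and the SAP. The CD3 sign is a wording correction.

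The size is modest. One of the 8 markers in one secondary endpoint is at risk of being lost, one has an unclear analyte, and one needs a sign aligned. VEGF is also in the protocol's sub-analysis list. No primary endpoint is touched. The point deserves correction because the remedy is cheap and a missed baseline cannot be recovered.

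The VEGF conclusion assumes that sites order tests from Table 2 and that no laboratory manual outside these documents adds VEGF to the draws.

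**What to change.** If sampling is still open:

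- Add VEGF to Table 2 footnote 2, at Days 0, 3, 7 and 10.
- Choose one creatine kinase analyte and name it identically in Table 2, the laboratory list, the Efficacy Assessments text, the protocol's endpoint lists, and SAP 2.1 and 7.2.1.

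The protocol is dated June 2020, the SAP is a November 2022 draft, and SAP 5.6 speaks of interim analyses in the past tense. Sampling may therefore be complete, although neither document says so. In that case:

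- Check the laboratory records for Day 0 VEGF. Where it was not drawn, report the endpoint as not collected, with the reason, and do not analyse it from later samples alone. Keep it visible in the report as a prespecified endpoint.
- Name in the SAP the creatine kinase analyte that was actually assayed.

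In either case, align the CD3 sign in the protocol's sub-analysis list with the assay in Table 2, Efficacy Assessments and the laboratory list.

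The cost is wording in one table footnote, a few lists and the SAP. If sampling is open, it adds one analyte, already on the laboratory list, at four draws that already take place, with no extra visit. If sampling is complete, it is a check of laboratory records before the SAP is finalised.

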9.3.5 Unscheduled Visits

The Investigator may at his/her discretion arrange for a patient to have an unscheduled assessment, especially in the case of adverse events (AEs) that require follow-up, or an AE considered by the Investigator to be possibly related to the use of the investigational product. The unscheduled visit page in the CRF must be completed.

10. Efficacy Assessments

7-Point Ordinal Scale

The ordinal scale is an assessment of the clinical status at the first assessment of a given study day. The scale is as follows:

- 1) Death
- 2) Hospitalized, on invasive mechanical ventilation or extracorporeal membrane oxygenation (ECMO)
- 3) Hospitalized, on non-invasive ventilation or high flow oxygen devices
- 4) Hospitalized, requiring supplemental oxygen
- 5) Hospitalized, not requiring supplemental oxygen
- 6) Not hospitalized, limitation on activities
- 7) Not hospitalized, no limitations on activities.

Complete Blood Count with Differential

The evaluation of the Complete Blood count with differential will help suspect the presence of a bacterial or viral infection with the predominance of either the neutrophils or lymphocytes. Generally, a healthy person’s blood count would not show out of range values in the differential in the absence of a pathological condition.

Comprehensive Metabolic Panel

The evaluation of glucose, calcium, proteins, electrolytes, liver enzymes and kidney function to determine status of metabolism. This panel is used to determine if treatments are having an effect on metabolic function.

CRP

C-reactive protein is considered to be an "acute phase protein," an early indicator of infectious or inflammatory conditions. CRP must be interpreted in the clinical context; no single value will be used to rule in or rule out a specific diagnosis.

CD4+/CD8+ ratio

The CD4+/CD8+ ratio is the ratio of T helper cells (with surface marker CD4) to cytotoxic T cells (with surface marker CD8). The CD4+/CD8+ ratio in the peripheral blood of healthy adults and mice is about 2:1, an inverted CD4+/CD8+ ratio (namely, less than 1/1) indicates an impaired immune system. A reduced CD4+/CD8+ ratio is associated with reduced resistance to infection, with ageing, and is an indicator of immunosenescence.

Natural Killer Cell Surface Antigen (CD3-CD56+ Marker Analysis)

Percentage CD3-CD56+ natural killers (NK⁺); absolute CD3-CD56+ natural killers (NK⁺); absolute lymphocyte count.

TNF-a

The primary role of TNF is in the regulation of immune cells. TNF, being an endogenous pyrogen, is able to induce fever, apoptotic cell death, cachexia, inflammation and to inhibit tumorigenesis and viral replication and respond to sepsis via IL1- & IL6-producing cells.

IL-6

Interleukin 6 (IL-6) is an interleukin that acts as both a pro-inflammatory cytokine and an anti-inflammatory cytokine. In humans, it is encoded by the *IL6* gene.

IL-10

IL-10 is a cytokine with multiple effects in immunoregulation and inflammation. It downregulates the expression of Th1 cytokines, MHC class II antigens, and co-stimulatory molecules on macrophages. It also enhances B cell survival, proliferation, and antibody production.

VEGF

VEGF is vascular endothelial growth factor. It is a signal protein produced by cells to stimulate angiogenesis. Increased levels of VEGF in the blood can indicate increased inflammation.

D-dimer

D-dimer is a protein fragment produced by dissolution of blood clots. Levels detectable in blood indicate clot formation and degradation within the system.

Myoglobin

A cytoplasmic protein that binds oxygen on a heme group. Functions to store oxygen. Increased myoglobin occurs when muscle tissue is damaged.

Troponin

A regulatory protein involved in muscle contraction. Can be used to indicate damage to myocardium. Increased troponin indicates recent cardiac muscle damage.

Creatinine Kinase

An enzyme involved in conversion of creatine in tissues that rapidly consume ATP, such as muscle. Higher levels of creatinine kinase are measured in the blood to identify damage to these tissues, such as myocardial infarction.

Serum Ferritin

An intracellular protein involved in iron storage. This test is generally used as a diagnostic for iron-deficiency anemia. High levels of serum ferritin may also indicate an acute inflammatory reaction, such as infection.

PCR nasopharyngeal swab

To detect viral target for Human Coronavirus (SARS-CoV-2), which would indicate active infection. If a subject with a previous positive PCR result obtains two negative PCR results consecutively, they are considered clear of active infection.

Safety Assessments

Safety assessments (vital signs, weight, physical examinations, EKG recordings, AEs, routine clinical laboratory tests (CBC, CMP, PT, PTT/INR and urinalysis) and chest x-rays will be performed at the visits specified in the schedule of assessments in Table 2.

Vital Signs, Height, and Weight

Vital signs (body temperature, pulse, oxygen saturation, systolic and diastolic blood pressure measurements) will be evaluated at the visits indicated in the schedule of assessments. It is important that all vital signs be measured after the patient has been resting in a sitting position for at least 5 minutes. Blood pressure measurements are to be taken in the same arm for the duration of the study. Body weight (without coats and shoes) will be recorded whenever vital signs are recorded, and height (without shoes) will be recorded at screening only.

Vital sign measurements will be repeated if clinically significant or machine/equipment errors occur. Out-of-range blood pressure and pulse measurements will be repeated at the Investigator's discretion. Any confirmed, clinically significant vital sign measurements will be recorded as AEs and followed up as such.

Physical Examination

A complete physical examination (head, eyes, ears, nose, throat, heart, lungs, abdomen, skin, cervical and axillary lymph nodes, neurological, and musculoskeletal systems) will be performed at screening. In addition, medical history (including smoking history) will be recorded at screening.

A limited physical examination to verify continued patient eligibility and to follow up any change in medical history will be performed at the visits indicated in the schedule of

assessments. Symptom-driven physical examinations will be performed as clinically indicated at any study visit. All changes not present at baseline or described in the past medical history and identified as clinically noteworthy will be recorded as AEs.

Electrocardiogram

A 12-lead resting EKG will be obtained at screening and at the early discontinuation visit, if applicable. At screening, the Investigator will examine the EKG traces for signs of cardiac disease that could exclude the patient from the study. An assessment of normal or abnormal will be recorded and if the EKG is considered abnormal, the abnormality will be documented in the CRF. EKGs will be repeated if clinically significant abnormalities are observed or artifacts are present.

Clinical Laboratory Parameters

The Investigator must review all laboratory reports and document the review. Any laboratory test result or change considered by the Investigator to be clinically significant should be considered an AE and recorded in the AE CRF. Clinically significant abnormal values occurring during the study will be followed until repeat test results return to normal, stabilize, or are no longer clinically significant.

Laboratory tests to be performed during the study:

Complete Blood Count with Differential	Natural Killer Cell Surface Antigen (CD3 ⁻ CD56 ⁺ Marker Analysis)
Complete Metabolic Profile	Il-10
Coagulation study (PTT/PT/INR)	CD4+ / CD8+ ratio
Urinalysis with pregnancy test	Creatine Kinase (CK)
C Reactive Protein	Troponin
Tumor Necrosis Factor alpha	Myoglobin (MB)
D-Dimer	VEGF
	Serum Ferritin

Adverse Events

An AE is any symptom, physical sign or disease that either emerges during the study or, if present at screening, worsens during the study, regardless of the suspected cause of the event. All medical and psychiatric conditions (except those related to the indication under study) present at screening will be documented in the medical history CRF. Changes in these conditions and new symptoms, physical signs, or diseases should be noted on the AE CRF during the rest of the study.

Clinically significant laboratory abnormalities should also be recorded as AEs. Surgical procedures that were planned before the patient enrolled in the study are not considered AEs if the conditions were known before study inclusion; the medical condition should be reported in the patient's medical history. Changes from baseline respiratory rate for non-ventilated subjects should also be considered as AE.

Serious Adverse Events (SAE)

A serious adverse event (SAE) is any AE that is:

- fatal
- life-threatening
- requires or prolongs hospital stay
- results in persistent or significant disability or incapacity
- Important Medical Events (IME): those events that may not result in death, be immediately life threatening, or require hospitalization. They may be considered a SAE when, based upon medical judgement, they may jeopardize the subject and may require intervention to prevent one of the other serious outcomes noted above. For example, drug overdose or abuse, a seizure that did not result in in-patient hospitalization, or intensive treatment of bronchospasm in an emergency department would typically be considered serious. (FDA, 21CFR312.32; ICH E2A and ICH E6)

All SAEs must be reported to Hope Biosciences Stem Cell Research Foundation immediately after the Investigator becomes aware of the event, along with a determination as to whether it is associated with the study drug.

Patients will be instructed to report AEs at each study visit. All AEs are to be followed until resolution or until a stable clinical endpoint is reached.

Each AE is to be documented in the CRF with reference to onset date, duration, frequency, severity, relationship to study drug, treatment of event, and outcome. Furthermore, each AE is to be classified as being serious or non-serious. Changes in AEs and resolution dates are to be documented in the CRF.

For the purposes of this study, the period of observation for collection of AEs extends from the time the patient gives informed consent through day 28 (or early discontinuation visit). Follow-up of the AE is required until the event resolves or stabilizes at a level acceptable to the Investigator.

Intensity of Adverse Event

The intensity of the AE will be judged based on the following:

- Mild: Awareness of sign(s) or symptom(s) which is/are easily tolerated
- Moderate: Enough discomfort to cause interference with usual activity
- Severe: Incapacitating or causing inability to work or to perform usual activities

Causal Relationship of Adverse Events

Medical judgement will be used to determine the relationship, considering all relevant factors, including pattern of reaction, temporal relationship, de-challenge and confounding factors such as concomitant medication, concomitant disease and relevant history. Assessment of causal relationship will be recorded in the CRF.

- **Definitely Related:** The adverse event is clearly related to the investigational product – i.e. an event that follows a reasonable temporal sequence from administration of the study intervention, follows a known or expected response pattern to the suspected intervention, that is confirmed by improvement on stopping and reappearance of the event on repeated exposure and that could not be reasonably explained by the known characteristics of the subject's clinical state.
- **Possibly Related:** An adverse event that follows a reasonable temporal sequence from administration of the study intervention follows a known or expected response pattern to the suspected intervention, but that could readily have been produced by a number of other factors.
- **Not Related:** The adverse event is clearly not related to the investigational product. - i.e. another cause of the event is most plausible; and/or a clinically plausible temporal sequence is inconsistent with the onset of the event and the study intervention and/or a causal relationship is considered biologically implausible.

Investigator Reporting: Notifying the Study Sponsor

Any study-related unanticipated problem posing risk to subjects or others, and any type of serious adverse event, will be reported to Hope Biosciences Stem Cell Research Foundation (Sponsor) by telephone within 24 hours of the event. To report such events, a Serious Adverse Event (SAE) form will be completed by the investigator and electronically faxed to the sponsor within 24 hours to [contact]. The investigator will keep a copy of this SAE form on file at the study site.

Within the following 48 hours, the investigator will provide further information on the Serious Adverse Event or unanticipated problem in the form of a written narrative. This should include a copy of the completed Serious Adverse Event form, and any other diagnostic information that will assist the understanding of the event. Significant new information on ongoing Serious Adverse Events should be provided promptly to Hope Biosciences Stem Cell Research Foundation.

Routine Study Close-out

The study will end when Hope Biosciences Stem Cell Research Foundation has obtained all data necessary to complete its studies of the investigational product. Standard procedures may include, but is not limited to, review of regulatory documents, collection of completed case report forms, reconciliation of study records, removal or destruction of ancillary study supplies,

and informing the Investigator of remaining obligations (e.g., record retention, final report submission to the IRB, financial disclosure updates, etc.).

Infusion Stopping Rules

Infusion will be stopped when:

- Allergic reaction is aroused after the product has been administered intravenously.
- Patient verbally decline the treatment at any moment prior, or during the infusion.
- Hyperpyrexia develops after infusion administration begins (core body temperature greater than or equal to 40°C) [59].
- PI may stop the study at any time, based upon PI's discretion
- Systolic blood pressure (sbp) ≥ 170 or diastolic blood pressure (dbp) ≥ 90 and sbp ≤ 90 or dbp ≤ 60
- Sudden Severe Hypotension (30-40 mm/Hg drop from pre-infusion level)
- Elevation or decrease in pulse of 20 bpm or more from baseline
- Change from baseline respiration rate in non-ventilated subjects

Study Alteration Rules

If any of the following events listed below occur, administration of the study drug will be immediately suspended. The Internal Monitoring Committee (IMC), presided by the Medical Monitor will meet to review the incident and its etiology. The committee determine if it is likely related to the drug, the infusion or unrelated. If the IMC along with the Medical Monitor agree that the SAE is unlikely or unrelated to the drug, the study will be continued. If the SAE appears to be definitely drug-related, the study will be stopped. If the SAE is probably or possibly linked to the drug, the IMC will determine the risk to future patients and decide if the study should proceed or be stopped.

Study Stopping Rules

The stopping rules listed below will trigger cessation of enrollment and potential study closure pending a comprehensive DSMB safety review.

1. Any infusion related death, deemed by PI to be associated or possibly associated with study drug.
2. Three or more of the same Grade 3 or higher AEs (judged by the investigator, medical monitor or sponsor), including infusion site reactions.
3. Any event which, in the opinion of the investigator, medical monitor or sponsor, contraindicates further dosing of additional subjects.
4. An infusion related, sustained (over 1 minute) episode of hypoxia (SaO₂ of less than 80%).
5. Any Grade 4-5 Adverse Event as defined in the NCI CTCAE v4.0 and determined to be temporally related to the HB-adMSC infusion by the Medical Safety Monitor and/or DSMB.

After such review, resumption of dosing may be considered, including consideration for any prophylactic interventions (e.g. antihistamines or corticosteroids for injection site reactions).

Medical Monitoring

Medical Monitor

It is the responsibility of the Principal Investigator to oversee the safety of the study at his/her site. This safety monitoring will include careful assessment and appropriate reporting of adverse events as noted above. At Hope Biosciences Stem Cell Research Foundation, [name], MD [contact] will be responsible for reviewing any reported AEs and SAEs to determine if changes to the study need to be made or if the study should be stopped for the protection of patients.

Data Safety Monitoring Board

